4.2. Method of Data Analysis

Exploratory and descriptive analysis will be completed for all study variables. Variables will be examined for normality and examined with means and standard deviations or medians and interguartile ranges accordingly. Statistical analyses will be conducted using a data management and analysis platform. Summary descriptive statistics will be analyzed for the main outcome variables. To examine the research question, an independent sample t-test will be conducted to assess if differences exist on pain and anxiety by Intervention or Control Group. An independent samples t-test is the appropriate statistical test when the purpose of research is to assess if differences exist on a continuous (interval/ratio) dependent variable by a dichotomous (2 groups) independent variable. The assumptions of normality and homogeneity of variance will be assessed. Normality assumes that the scores are normally distributed (bell-shaped) and will be assessed using the one-sample Shapiro-Wilk test (Razali & Wah, 2011). Homogeneity of variance assumes that both groups have equal variances and will be assessed using Levene's test for equality of variances (Levene, 1960). If the Levene's test for equal variance indicates that equal variances cannot be assumed ($p \le .05$), a Welch's t-test will be used instead of the Student's t-test, which is more reliable when the two samples have unequal variances (Ruxton, 2006). The t-test will be two-tailed with the probability of rejecting the null hypothesis when it is true set at p < 0.05. This ensures a 95% certainty that the differences did not occur by chance.

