1.2. Hypothesis

Hypothesis: Scheduled cesarean delivery patients receiving a Healing Touch (HT) intervention will report decreased levels of pain and anxiety when compared to a control group. Study Aims

Aim 1: To test the efficacy of a Healing Touch intervention on pain scores among scheduled cesarean delivery patients.

Hypothesis 1: Scheduled cesarean delivery patients will report lower pain scores after receiving a Healing Touch intervention when compared to a control group.

Aim 2: To test the efficacy of a Healing Touch intervention on anxiety scores among scheduled cesarean delivery patients.

Hypothesis 2: Scheduled cesarean delivery patients will report lower anxiety scores after receiving a Healing touch intervention when compared to a control group.

Aim 3: Explore the feasibility of providing a HT intervention on an obstetrical unit.

This will be assessed and evaluated through the course of the study as to the number of patients that are approached and decide to enroll. The research team will also be monitoring how the HT sessions can best be integrated into the daily care of the study participants.

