3. STUDY METHODS AND PROCEDURES

3.1. Study Treatment/Intervention

If the woman completes the consent form, they will be enrolled in the study and randomized into either the intervention or control group. When they are admitted to the postpartum unit after cesarean delivery, based on their randomization, the study coordinator at each site will schedule either 1) a Healing Touch (HT) practitioner for the intervention group OR 2) a non-HT practitioner who will collect data for the control group. The HT practitioners for this study will be registered nurses or HT practitioners who work in the Inova Health System and have received the minimum of Foundations of Healing Touch training. All study personnel entering patient care areas will abide by universal precautions, plus masks and face shields as required by the hospital system for infection control. For the intervention group, the HT practitioner will verify consent. Then they will ask the woman to complete baseline measurements of pain and anxiety. The practitioner will then administer the HT intervention consisting of a full body, pain management technique focusing on the surgical site, and wound sealing. HT techniques (Field Repatterning, Pain Syphon, Beak Fingers Lasering,) are techniques specific to management of pain and clearing of the energy field that have been used frequently by the nurses in their delivery of patient care. The HT intervention to be used in the proposed study has been developed by co-investigator, [name], Certified Healing Touch Practitioner and Instructor, to focus on the symptom management needs of the study participants (post-cesarean delivery) and should take no more than 15 minutes to complete. Levels of pain and anxiety will be reassessed post-intervention. Nurses providing the HT intervention will document the session and other outcomes as described below. There is a risk that the patient will not receive Healing Touch if: there is not a HT provider available or the patient is discharged prior to availability of the HT provider.

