3.2. Control Group

This study has a control group. For the control group: a member of the research team, who may or not be a HT practitioner, will verify consent. Then they will ask the woman to complete baseline measurements of pain and anxiety. The subject will then be encouraged to have a quiet time session equivalent to the length of a Healing Touch session, with the lights dimmed. After the quite time, the team member will again measure the subject's levels of pain and anxiety.

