3.4. Endpoints/Outcomes Measurements

3.4.1.Primary outcomes.

Primary outcomes will include the differences between the intervention and control groups' pre-/postintervention levels of pain (Numeric Rating Scale) and anxiety (Numeric Rating scale) (Appendix K).

Theoretical Concept and Measurement	#	Score	Reliability
	Items	Range	
Demographics			
As delineated in Data Retrieval Form	12		
Pain (Primary outcome)			
Visual Analog Scale: Measures pain intensity. Higher scores indicate higher levels of pain	1	0-10	* r =0.96 literate patients r= illiterate
Anxiety (Primary outcome)			
Hospital Anxiety Scale: Measures intensity of anxiety. Higher scores indicate higher levels of anxiety	16	0-14	Cronbach's alpha 0.73**
Healing Touch			-

* (Hawker, Mian, Kendzerska, & French, (2011). * Ferraz., Quaresma, Aquino, Atra, Tugwell, P., & Goldsmith, 1990).

**Al Aseri, Suriya, Hassan, Hasan, Sheikh, Al Tamimi, Alshathri M, Khalid N. (2015).

3.4.2.Secondary outcomes

Secondary outcomes include the relationship between HT and demographic information of the subjects. As well, the feasibility of introducing HT as a therapy for postpartum women will be assessed.

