3.5. Consent/Assent

All participants in the HT intervention group and control group will provide informed consent. Acquiring consent is a twostep process: (1) Participant returning and electronic consent via the survey platform, and then (2) the site PI/SUB-I has a conversation with the participant over the phone or face to face to review the consent. Once screened for eligibility, a member of the research team may call the potential participant using the consent phone call script (Appendix H). Whether over the phone or face to face, the study personnel will describe the study, answer any questions they may have, and if the participant is interested, email them an electronic consent form and the HIPPA authorization form if they haven't already received one. Both of these forms will be managed through an electronic platform, and securely load into the platform to be accessed by

the PI and study personnel. Participants who complete the electronic consent form will be included in the study, and randomized into either the intervention or control group. Informed consent will be confirmed again with the women prior to starting the study intervention or control session, since they may have changed their mind after delivery. One copy of the consent and HIPAA forms will be given to the participant (via email or face to face), and one will be kept in the research file for the participant, as well as being scanned into the electronic medical record.

3.6. Monitoring Subjects and Criteria for Withdrawal of Subjects from the Study.

Study participants may voluntarily withdraw from the study at any time. During the Healing Touch Therapy, the intervention would stop and a subject would be withdrawn if: The woman or her family at the bedside requested the intervention stopped, the woman reported an increase in pain and needs assistance, the woman had a self-identified change in clinical status and requested medical assistance, the woman needs to stop the session to care for the baby or get out of bed / leave the room for some reason.

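### Section 4.2 does not say whether the post-session or the change score is tested and does not adjust for the pre-session score; a baseline-adjusted model would be a cheap gain in precision and pre-specification.

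*Combined protocol and SAP*

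**What the plan says.** Section 4.2 gives the whole primary analysis: "an independent sample t-test will be conducted to assess if differences exist on pain and anxiety by Intervention or Control Group". Welch's test replaces Student's if Levene's test gives p of 0.05 or less. The test is two-tailed at 0.05. No covariate is named, and the dependent variable is not defined beyond pain and anxiety.

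Other sections describe the score in two ways:

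- Section 3.4.1, and the abstract in the same words, define the primary outcomes through group differences in "pre-/postintervention levels of pain (Numeric Rating Scale) and anxiety (Numeric Rating scale", which leans to a change score. The overall hypothesis in 1.2 ("will report decreased levels of pain and anxiety when compared to a control group") leans the same way.
- Hypothesis 1 in 1.2 reads "Scheduled cesarean delivery patients will report lower pain scores after receiving a Healing Touch intervention when compared to a control group". Hypothesis 2 says that patients "will report lower anxiety scores after receiving a Healing touch intervention when compared to a control group". Both lean to the post-session score.

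A pre-session score exists in both arms. Section 3.1 says: "For the intervention group, the HT practitioner will verify consent. Then they will ask the woman to complete baseline measurements of pain and anxiety". Section 3.2 has the same step for controls: "Then they will ask the woman to complete baseline measurements of pain and anxiety". Randomisation comes earlier, at consent (3.5): "Participants who complete the electronic consent form will be included in the study, and randomized into either the intervention or control group".

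Section 4.1 sizes the trial for an independent-samples t-test with d = 0.5, two-sided alpha 0.05 and power 0.80. This gives 64 per arm, with recruitment of 160. It does not say which score d refers to.

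**The concern.** Each primary outcome has two defensible t-tests, one on the post-session score and one on the change, and the plan does not choose. The two have different variances and can give different answers on the same data, so the choice should be fixed before the data are seen.

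Separately, the pre-session score is probably correlated with the post-session score. A model with it as covariate uses that correlation at no cost in women. At stake are the width of the confidence interval and the clarity of the primary result, not the validity of the test.

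**Working it through.** **Inputs from the documents (4.1, 4.2):** d = 0.5, two-sided alpha 0.05, power 0.80, equal allocation, 64 per arm. **Assumed, because the documents do not give them:** pre-post correlation r = 0.3, 0.5 or 0.7, and equal pre and post SDs unless stated.

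**1. The plan's own figure.** The noncentral t with 2n − 2 degrees of freedom and noncentrality d·√(n/2) = 0.5·√32 = 2.83 gives power 0.801 at 64 per arm and 0.795 at 63. The stated 128 is reproduced. With all 160 analysed, 80 per arm, the t-test has power 0.88.

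**2. The adjusted model removes the choice of score.** If post = a + b·arm + c·pre, then post − pre = a + b·arm + (c − 1)·pre. The arm coefficient b is the same either way.

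**3. Precision, which needs no d.** In units of the post-score variance, the variance factors are 1 (post), 2(1 − r) (change) and 1 − r² (adjusted). The interval-width ratios are √(1 − r²) against post and √((1 + r)/2) against change.

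| | r = 0.3 | r = 0.5 | r = 0.7 |
|---|---|---|---|
| Adjusted / post | 0.954 | 0.866 | 0.714 |
| Adjusted / change | 0.806 | 0.866 | 0.922 |

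The adjusted interval is thus 5%/13%/29% narrower than the post-score one and 19%/13%/8% narrower than the change-score one. This ignores one degree of freedom and a small cost of chance baseline imbalance.

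**4. Power at 64 per arm** (noncentral t; 2n − 3 degrees of freedom for the adjusted model).

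| | r = 0.3 | r = 0.5 | r = 0.7 |
|---|---|---|---|
| d on post SD: post t-test | 0.80 | 0.80 | 0.80 |
| d on post SD: change t-test, d/√(2 − 2r) | 0.66 | 0.80 | 0.95 |
| d on post SD: adjusted, d/√(1 − r²) | 0.84 | 0.90 | 0.98 |
| d on change SD: change t-test | 0.80 | 0.80 | 0.80 |
| d on change SD: adjusted, d·√(2/(1 + r)) | 0.94 | 0.90 | 0.86 |

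**5. Where the gain vanishes.** Let k be the baseline SD divided by the post SD, with d on the change SD. The adjusted effect size is 0.5·√(1 + k² − 2rk)/√(1 − r²). At r = 0.7 and k = 0.8 it is 0.5·√0.52/√0.51 = 0.505, power 0.809 against 0.801. At k = 0.7 the two square roots are equal (both √0.51) and there is no gain.

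**6. Cost of a post-randomisation baseline.** Assume that knowledge of allocation shifts the mean baseline report in one arm by 0.2 SD with no matching shift afterwards. The bias is 0.2·r = 0.06/0.10/0.14 SD for the adjusted model, 0.20 SD for the change score and 0 for the post-score test. The simulated false-positive rates (200,000 trials per r, 64 per arm) are 0.06/0.10/0.19, 0.16/0.20/0.30 and 0.05.

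**The case against.** The case for leaving the analysis alone is a fair one. The t-test is valid, the sample size is right, and omitting a covariate is not an error. The outcome definition in 3.4.1 most naturally means change, and one sentence in 4.2 would settle the score. The size of the gain rests on r, on the SDs and on the scale of d, none of which is in the documents. Adjustment also exposes the result to a baseline reported after randomisation, whereas the post-score t-test is immune to that.

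Most of this stands as a limit on the claim. Naming the score would close the pre-specification gap, but the precision gap would remain. The exposure to a shifted baseline is real, though smaller than that of the change score, which the plan also permits. The 0.2 SD shift is an illustration that no section supports.

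A reader might infer three stronger things, and the documents support none of them:

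- **That baseline goes unused.** On the change-score reading of the abstract and 3.4.1 it enters by subtraction, and 4.2 plans descriptive analysis of all study variables. What can be said is that it is not a covariate.
- **That the trial is underpowered.** The 0.66 above arises only if d = 0.5 is on the post-score SD and change is tested. Section 4.1 does not fix the scale. If d refers to whichever score is tested, power is 0.80 either way.
- **That false positives will be inflated by picking the better of two tests.** No section plans to run both and report the smaller p-value.

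**Conclusion.** The point holds as a cheap improvement in precision and pre-specification. Section 4.2 leaves the primary score unnamed while other sections lean both ways, and it does not adjust for a baseline already collected in both arms. The adjusted model gives one treatment effect under either reading and, apart from the small costs noted, is at least as precise as either t-test. Over the assumed range of r with equal SDs, intervals narrow by 5% to 29% against the post score and by 8% to 19% against change. Power at 64 per arm rises from 0.80 to between 0.84 and 0.98. The power gain can be close to nil if d is on the change score and the baseline SD is well below the post SD.

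The change should be made, but the plan is not wrong without it. Confidence is medium, because r and the SDs are assumed and because preferring the adjusted model over the post-score test, given a baseline taken by the treating practitioner with no blinding described, is a judgement.

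**What to change.** State in 4.2 that, for each primary outcome, the single decisive analysis is a linear model of the post-session score on arm and the pre-session score of the same instrument, reported as an adjusted mean difference with 95% CI and a two-sided test at 0.05. Make an unadjusted Welch t-test on the post-session score the sensitivity analysis, and report baseline means and SDs by arm. State the limitation beside it: baseline follows randomisation, is taken by the treating practitioner in the Healing Touch arm, and no blinding is described.

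Align the abstract, 1.2 and 3.4.1 with that outcome, and say in 4.1 which score d = 0.5 refers to. Reconcile the instruments in 3.4.1 first: the text names Numeric Rating Scales, and the table names a Visual Analog Scale and the Hospital Anxiety Scale.

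If the team prefers to keep the t-test, one sentence naming the score closes the pre-specification gap but not the precision gap.

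The cost is protocol and SAP wording and one regression per outcome, with no new data and no extra women. The one statistical cost is the exposure to an allocation-driven baseline shift shown in step 6. The change does not deal with women who consent but have no session, or with having two primary outcomes.

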4. STATISTICAL CONSIDERATIONS/DATA ANALYSIS

4.1. Sample Size

Power analysis for an independent sample t-test was conducted in G-POWER to determine a sufficient sample size using an alpha of 0.05, a power of 0.80, a medium effect size (d = 0.5), and two tails. There will be an equal allocation of participants into each group. Based on the aforementioned assumptions, the desired sample size is 128 (64 in each group). The team will over sample in order to meet sufficient sample size. Planned recruitment will = 160 women (40 per study site).

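### Section 4.2 reads a 0.05 significance level as 95% certainty that a difference is real; this is false for one t-test, and the 5% does not cover two primary outcomes each tested at 0.05

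*Combined protocol and SAP*

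**What the plan says.** Section 4.2 (Method of Data Analysis) plans an independent-samples t-test for pain and another for anxiety, with Welch's version if Levene's test rejects equal variances. It states the error rate properly: "The t-test will be two-tailed", with "the probability of rejecting the null hypothesis when it is true set at p < 0.05". The next sentence explains what this achieves: "This ensures a 95% certainty that the differences did not occur by chance".

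Section 3.4.1 opens "Primary outcomes will include the differences between the intervention and control" groups before and after the session, and it names both pain and anxiety as primary. Section 1.2 gives each its own aim and numbered hypothesis. No section states a multiplicity adjustment, a testing order or a rule that both outcomes must be significant. Section 4.1 sizes the trial for one t-test, "using an alpha of 0.05, a power of 0.80, a medium effect size (d = 0.5), and two tails", which leads to 128 women (64 per group) and planned recruitment of 160. Section 4.2 plans no confidence interval for the between-group difference.

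**The concern.** The two adjacent sentences in section 4.2 do not agree. The first is a probability calculated on the assumption that there is no effect. The second turns it into a probability that an observed difference is real. These are different quantities, and the second cannot be obtained from alpha alone.

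There is also a question of scope. Even as an error rate, 5% describes one test. The trial has two primary tests at that level, and nothing in the plan prevents an efficacy claim from resting on either one. A reader who relies on the sentence would put more weight on a single p-value below 0.05 than the design supports. Because no confidence interval is planned, nothing else in the section would show how precise the estimate is.

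**Working it through.** **Inputs.** From section 4.1: alpha 0.05 two-sided, power 0.80, d = 0.5, equal allocation, 64 per group, 160 planned. From sections 1.2 and 3.4.1: two primary outcomes with separate hypotheses. From section 4.2: each is t-tested at 0.05. The documents do not give the prior probability of a true effect (π) or the correlation between the pain and anxiety test statistics (r). Both are assumptions here and are shown as ranges.

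**1. The plan's own sample size.** Noncentral-t power for a two-sided two-sample t-test at d = 0.5 and alpha 0.05 is 79.5% with 63 per arm and 80.1% with 64. The stated 128 is therefore correct for one outcome at 0.05.

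**2. One test: does p < 0.05 give 95% certainty?** By Bayes' rule, with d = 0.5 as the true effect,

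P(effect | p < 0.05) = 0.80π / [0.80π + 0.05(1 − π)].

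- π = 0.1: 0.080 / (0.080 + 0.045) = 64%
- π = 0.3: 0.240 / (0.240 + 0.035) = 87%
- π = 0.5: 0.400 / (0.400 + 0.025) = 94%
- π = 0.6: 0.480 / (0.480 + 0.020) = 96%

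Setting the expression equal to 0.95 gives 0.04π = 0.0475(1 − π), so π = 0.0475 / 0.0875 = 0.54. The stated certainty therefore depends on a prior of at least about 0.54 together with the full 80% power.

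**3. Two tests: the chance of at least one false positive when neither outcome is affected.**

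- Independent: 1 − 0.95² = 9.75%
- r = 0.3: 9.5%
- r = 0.5: 9.1%
- r = 0.7: 8.3%

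The correlated values come from the bivariate normal distribution with two-sided 0.05 limits on each statistic. The rate falls to 5% only if the two statistics are perfectly correlated.

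**4. Power under Holm.** The smaller of the two p-values must be at or below 0.025. If it is, the other is tested at 0.05. Noncentral-t power at d = 0.5:

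| Per arm | At 0.05 | At 0.025 |
|---|---|---|
| 64 | 80.1% | 71.2% |
| 80 | 88.2% | 81.5% |

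The 0.025 column is the power for an outcome when the other does not reach significance. If both outcomes truly have d = 0.5 and are independent, the power for each is P(p₁ ≤ 0.025) + P(0.025 < p₁ ≤ 0.05) × P(p₂ ≤ 0.025):

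- 64 per arm: 0.712 + (0.801 − 0.712) × 0.712 = about 78%
- 80 per arm: 0.815 + (0.882 − 0.815) × 0.815 = about 87%

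Eighty percent power at 0.025 needs 78 per arm, or 156 women, which is within the 160 planned.

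**The case against.** The best defence is that the sentence is an explanatory gloss. The decision rule is the sentence before it, which is right, and deleting the gloss alters no test, threshold, sample size or data item. That stands. A reader might infer that the plan's rule for declaring success is itself wrong, or that the trial is committed to reporting 95% certainty. The documents support neither reading, since section 4.2 contains no reporting language of that kind. What remains is a stated property, in the operative analysis section, that the design does not have.

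A second defence is that the overall hypothesis in section 1.2 names pain and anxiety together and could mean that both must improve. In that case no alpha split is needed. But Hypotheses 1 and 2 are stated separately and no joint rule appears, so the point is open. Requiring both would not make the 95% sentence true. It would also have its own power cost: with 64 per arm and independent outcomes, 0.801² = about 64% for both.

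A third defence is that any calculation of how often significant results are false rests on assumed priors. That is fair. At a prior of 0.1 the figure is 36%, and a reader might take this as the trial's expected false-positive share. The documents give no prior, and at 0.6 the figure is 4%. The calculation shows only that alpha does not fix the answer.

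**Conclusion.** The sentence is wrong for a single test and conflicts with the correct definition just before it. The 95% would require a prior of at least about 0.54 at 80% power, which the documents do not provide. Across the two primary outcomes as planned, the chance of at least one false positive when neither is affected is 9.75% if independent and about 9.5% to 8.3% at assumed correlations of 0.3 to 0.7, against the 5% a reader would assume. This second part rests on reading pain and anxiety as separate routes to a claim, which Hypotheses 1 and 2 support and nothing in the plan excludes.

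A reader might also infer that the sample size is miscalculated or that the choice of t-test is at fault. The figures above do not show either: 128 reproduces for one outcome at 0.05. The correction should be made before analysis. It concerns what may be concluded from a significant result.

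**What to change.** In section 4.2, delete the sentence. Suggested replacement: The family-wise two-sided type I error across pain and anxiety is held at 5% by the Holm procedure; for each outcome the between-group mean difference is reported with its 95% confidence interval. If the sponsor means to require both outcomes, say that instead and leave each test at 0.05. Deletion alone would leave two unadjusted primary tests, and an adjustment alone would leave the false sentence in place, so both changes are needed.

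In section 4.1, state that 80% power with 64 per arm applies to one outcome at 0.05. Add that at the first Holm step power for a single outcome at d = 0.5 is about 71% with 64 per arm and 81% if all 160 are analysed 1:1, and that it is higher if both outcomes have a true effect.

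The cost is a revision to the text and a lower stated power, with no additional women. At 64 per arm the loss on a single outcome is about 9 percentage points (80.1% to 71.2%). The planned 160 offsets it only if at least 156 are analysed in a near-equal split.
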